### **5.4 Vital signs**

Vital signs are to be measured at Screening, pre-dosing and at various timepoints post-dosing on dosing days. At each of these times, resting systolic and diastolic blood pressure, pulse rate, respiratory rate, temperature, pulse oximetry, and pre-dosing transcutaneous carbon dioxide will be measured.

The number and percentage of subjects meeting selected criteria post-baseline and outliers will be summarized only for the integrated analysis.

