3. SYNOPSIS

This is a brief summary. For details, refer to the body of the protocol.

Protocol Number: 232SM202

Protocol Title: A Phase 2, randomized, double-blind, sham-procedure controlled study to assess the safety and tolerability and explore the efficacy of ISIS 396443 (BIIB058) administered intrathecally in subjects with spinal muscular atrophy who are not eligible to participate in the clinical studies ISIS 396443-CS3B or ISIS 396443-CS4

Version Number: 4

Name of Study Treatment: Nusinersen (also known as BIIB058 and ISIS 396443)
Note: For the purposes of this protocol, when referring to “study drug,” Nusinersen will be used in place of ISIS 396443. When referring to the protocol title or previous (“index”) studies, ISIS 396443 will be used. The term “study treatment” refers to administration of Nusinersen or the sham procedure during the blinded portion of the study.

Study Indication: Spinal muscular atrophy (SMA)

Phase of Development: 2

Study Rationale: The rationale of Part 1 of the study is to assess the safety and tolerability and evaluate the utility of selected exploratory efficacy endpoints in subjects with SMA treated intrathecally with Nusinersen who are not eligible for the clinical studies ISIS 396443-CS3B or ISIS 396443-CS4.

Based on emergent data from the Nusinersen clinical development program, the Sponsor may decide to terminate Part 1 early, and all subjects may be offered the opportunity to transition to Part 2 (the open-label extension phase) prior to completion of all Part 1 evaluations. The rationale of Part 2 of the study is to assess the long-term safety and tolerability of Nusinersen in subjects with SMA who participated in Part 1 and completed their End of Part 1 Evaluation assessments.

Study Objectives and Endpoints: **Part 1**

Primary objective:

The primary objective of Part 1 of this study is:

- To assess the safety and tolerability of Nusinersen in subjects

CONFIDENTIAL

The information contained herein may not be used, disclosed, or published without the written consent of Biogen MA Inc.

with SMA who are not eligible to participate in the clinical studies ISIS 396443-CS3B or ISIS 396443-CS4.

The primary endpoints that relate to this objective are:

- Incidence of adverse events (AEs) and serious AEs (SAEs)
- Change from baseline in clinical laboratory parameters, electrocardiograms (ECGs), and vital signs
- Change from baseline in neurological examination outcomes

Secondary objective:

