¹ A blood sample will be collected at Screening for *SMN2* copy number only from those subjects without genetic documentation of *SMN2* copy number. For all other subjects, a blood sample will be collected at any time during the study for analysis of *SMN2* copy number by the central laboratory.

² After the injection of study treatment or sham procedure on Day 1, subjects will remain at the study site for at least 24 hours (Day 2) for safety monitoring. On the day following the injection of study treatment or sham procedure on Days 15, 29, 64, 183, and 302, there will be safety monitoring through telephone contact. During that telephone contact (i.e., Days 16, 30, 65, 184 and 303), changes in concomitant medications and AEs, information on the subject’s daily ventilator/Bi-PAP use, and health status will be recorded.

³ End of Part 1 is one of the following: Part 1 Final Follow-up Evaluation (Day 422 [±7 days]) according to the study schedule, early Part 1 Final Follow-up Evaluation to allow for rollover into Part 2, or Early Termination Evaluation for subjects who withdraw from the study during Part 1.

⁴ For subjects not transitioning into Part 2, the date of the End of Part 1 Evaluation assessments will be the end of study. For subjects who transition to Part 2, the date of the End of Part 1 will be the date of first dose in Part 2.

⁵ At the End of Part 1 evaluation, in order to allow transition to Part 2, subjects will be unblinded.

⁶ Vital signs include resting systolic and diastolic blood pressure, pulse rate, respiratory rate, temperature, pulse oximetry, and transcutaneous carbon dioxide. Pulse oximetry and transcutaneous carbon dioxide will be measured predose at each evaluation. For subjects who are not receiving noninvasive ventilation, pulse oximetry will be measured overnight once a week at home.

⁷ Vital signs (resting systolic and diastolic blood pressure, pulse rate, respiratory rate, temperature, and pulse oximetry) will be collected at 4 timepoints: 1, 2, 4, and 6 hours (all ±15 minutes) after the injection of study treatment.

⁸ Vital signs (resting systolic and diastolic blood pressure, pulse rate, respiratory rate, temperature, and pulse oximetry) will be collected within 20 to 24 hours after the injection of study treatment or sham procedure.

CONFIDENTIAL

The information contained herein may not be used, disclosed, or published without the written consent of Biogen MA Inc.

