- ⁹ At the evaluations scheduled for injection of study treatment or sham procedure, subjects will be assessed for the following growth parameters: body length, head circumference, chest circumference, and arm circumference.
- ¹⁰ Neurological examinations include assessment of mental status, level of consciousness, sensory function, motor function, cranial nerve function, and reflexes.
- ¹¹ Neurological examinations will occur between 4 to 6 hours after the injection of study treatment or sham procedure.
- ¹² Blood chemistry, hematology, and urinalysis panels.
- ¹³ Samples for safety laboratory tests will be collected before the injection of study treatment or sham procedure on Days 64 and 183 only.
- ¹⁴ End of Part 1 safety laboratory tests may be performed locally in addition to centrally to accommodate the Part 2 Day 1 dosing.
- ¹⁵ Refer to [Table 5](#) for CSF PK sample schedule. The CSF samples will be analyzed for Nusinersen concentrations. The remaining CSF sample will be stored for optional future biomarker analyses.
- ¹⁶ Blood samples for PK assessment will be collected 4 hours (± 1 hour) after the injection of study treatment or sham procedure only on Day 1. Refer to [Table 5](#) for the plasma PK sample schedule.
- ¹⁷ Blood samples for PK assessment will be collected before the injection of study treatment or sham procedure on Days 64 and 183 only. Refer to [Table 5](#) for the plasma PK sample schedule.
- ¹⁸ Overnight stay (at least 24 hours) is required after the first injection of study treatment or sham procedure. Following all subsequent injections or sham procedures, a stay of at least 6 hours at the study site is required; overnight stays are optional on these days.
- ¹⁹ In addition to concomitant medications, ancillary procedures will be recorded.
- ²⁰ AEs and SAEs will be collected in the case report form from the time of signing of the informed consent form as described in [Section 15.3.1](#) and [Section 15.3.2](#).

CONFIDENTIAL

The information contained herein may not be used, disclosed, or published without the written consent of Biogen MA Inc.

4.2.2. Schedule of Events: Part 2

Table 3: Part 2 Schedule of Activities for Subjects Randomized to Receive Nusinersen in Part 1

Study Period	Part 2 Treatment/Follow-Up									
	Study Day	Day 1			Day 2 ¹	Days 120, 239, 358, 477, 596, 715 (± 7 days) ²			Days 121, 240, 359, 478, 597, 716 ¹	Part 2 Final Follow-Up (Day 835 [± 7 days]) ³ or Part 2 Early Termination ⁴

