- ⁸ Vital signs (resting systolic and diastolic blood pressure, pulse rate, respiratory rate, temperature, and pulse oximetry) will be collected at 4 timepoints: 1, 2, 4, and 6 hours (all ± 15 minutes) after the injection of study treatment only on Part 2 Day 1. On subsequent study days, vital signs will be collected 1 hour after the injection of study treatment.
- ⁹ Vital signs (resting systolic and diastolic blood pressure, pulse rate, respiratory rate, temperature, and pulse oximetry) will be collected on Day 2 within 20 to 24 hours after the injection of study treatment only.
- ¹⁰ At the evaluations scheduled for injection of study treatment, subjects will be assessed for the following growth parameters: body length, head circumference, chest circumference, and arm circumference. Growth parameters and weight are to be collected at the same time.
- ¹¹ Neurological examinations include assessment of mental status, level of consciousness, sensory function, motor function, cranial nerve function, and reflexes. If sedation was used, please allow sufficient recovery time for the subject to be fully engaged in the examination because it is important that the data collected truly reflect the subject's neurological performance.
- ¹² Predose and postdose.
- ¹³ ECG will be performed at Days 64, 183, 540, and 778, and at the Part 2 Final Follow-up Evaluation. ECG must be performed before obtaining blood samples for safety laboratory tests.
- ¹⁴ Blood chemistry, hematology, urinalysis, urine total protein panels, and coagulation parameters. Urine total protein and coagulation parameters will be assessed by local laboratories.
- ¹⁵ Samples for safety laboratory tests will be collected before the injection of study treatment at each dosing visit.
- ¹⁶ Blood samples for immunogenicity testing will be collected before the injection of study treatment on Days 64, 183, 302, 421, 540, 659, and 778.
- ¹⁷ Refer to [Table 7](#) for CSF PK sample schedule. The CSF samples will be analyzed for Nusinersen concentrations. The remaining CSF sample will be stored for optional future biomarker analyses.
- ¹⁸ Blood samples for PK assessment will be collected 4 hours (± 1 hour) after the injection of study treatment only on Day 1. Refer to [Table 7](#) for the plasma PK sample schedule. Plasma PK samples will be collected predose on Days 64, 183, 540, and 778.

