11.1.2. Sham Procedure

In Part 1 of the study, subjects randomized to the sham procedure control group will undergo a sham procedure, rather than study treatment administration, on Study Days 1, 15, 29, 64, 183, and 302. Details regarding the sham procedure will be provided in the DHA. The sham procedure will be administered by dedicated study personnel who are unblinded to treatment group; this cannot be any of the key study site personnel (i.e., the Investigator, study coordinator, or outcomes assessors). The sham procedure in Part 1 will be performed in a dedicated room, and key study personnel and the parent or legal guardian will not be present during the procedure to ensure blinding.

In general, the sham procedure in Part 1 will consist of a small needle prick on the lower back at the location where the LP injection is normally made. The needle will break the skin, but no LP injection or needle insertion will occur. The needle prick will be covered with the same bandage that is used to cover the LP injection normally, thus simulating the appearance of an LP injection. If institutional guidelines require the use of anesthesia or sedation for an LP procedure in Nusinersen-treated subjects, then in order to maintain the blind, minimal sedation (i.e., a low dose of an anxiolytic) should be used for the sham procedure in Part 1, following institutional procedures. The study subject will be kept in the procedure room for the same amount of time that subjects administered study treatment are kept, thus simulating the time period of the study treatment administration procedure.

Study treatment and sham kits will be packaged in a blinded fashion. Blinded kits for the sham procedure in Part 1 contain artificial CSF (5.0 mL solution per 6 mL vial) that will not be injected but will be used to simulate CSF samples for that subject.

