Summary statistics will be presented throughout. For continuous endpoints, summary statistics will generally include number of subjects with data, mean, standard deviation, median, minimum and maximum. The mean changes from baseline will be estimated with 95% confidence intervals. For categorical endpoints, summary statistics will generally include: number of subjects dosed, number of subjects with data, and the percentage of those with data in each category. Frequency distributions will be presented as appropriate.

The statistical software, SAS® version 9.4 or above, will be used for all summaries and statistical analyses.

For Part 2, a limited number of summaries will be produced. The approach will be to preserve the Part 1 study groupings as follows for Safety and Efficacy population:

- Previous control.
- Previous ISIS 396443.
- Total (previous control and previous ISIS 396443).

For the integrated analyses, the Safety displays will be grouped as follows:

- Previous control, Part 1, from their first sham procedure in Part 1.
- Previous control, Part 2, from their first ISIS 396443 dose in Part 2.
- Previous ISIS 396443, Part 1 and 2, from their first ISIS 396443 dose in Part 1.
- Total (Previous control Part 2 and previous ISIS 396443 Part 1 and 2)

For the integrated analyses, the Efficacy displays will be grouped as follows:

- Previous control, Part 1, from their first sham procedure in Part 1.
- Previous control, Part 2, from their first ISIS 396443 dose in Part 2.
- Previous control, Part 1 and 2, from their first sham procedure in Part 1.
- Previous ISIS 396443, Part 1 and 2, from their first ISIS 396443 dose in Part 1.

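### SAP 5.4 counts children who ever meet a vital-sign criterion, but the integrated safety columns are scheduled for different numbers and timing of readings (22, 10 to 14, and 29 after the procedure), so the percentages partly reflect monitoring intensity

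*SAP*

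**What the plan says.** SAP 5.4 gives one specific summary for vital signs: "The number and percentage of subjects meeting selected criteria post-baseline and outliers will be summarized only for the integrated analysis". The criteria are not listed. The integrated windowing rule in SAP 4.1 names HINE, growth, CGI, laboratory and concentration data, but not vital signs.

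SAP 2 sets four integrated safety columns: Previous control in Part 1 (sham), Previous control in Part 2 (nusinersen), Previous ISIS 396443 in Parts 1 and 2, and "Total (Previous control Part 2 and previous ISIS 396443 Part 1 and 2".

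The schedules behind these columns are in Protocol 4.2.

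- **Part 1 (Table 2).** Procedures fall "on Study Days 1, 15, 29, 64, 183, and 302". Where the table shows 4X, vital signs "will be collected at 4 timepoints: 1, 2, 4, and 6 hours"; this covers Days 1, 29, 64, 183 and 302. Day 15 has a single post-dose mark with no stated hour. The Day 2 reading "will be collected within 20 to 24 hours after the injection of study treatment or sham procedure". Sham children follow the same schedule, because study treatment "refers to administration of Nusinersen or the sham procedure during the blinded portion of the study".
- **Part 2, previous sham (Table 4).** Day 1 keeps the 1, 2, 4 and 6 h readings and Day 2 keeps the 20-24 h reading. After that, "On subsequent study days, vital signs will be collected 1 hour after the injection of study treatment".
- **Part 2, previous nusinersen (Table 3).** There is one reading at 1 h after each dose.

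For the post-dose neurological examination, Part 1 fixes the hour: "Neurological examinations will occur between 4 to 6 hours after the injection of study treatment or sham procedure". The Part 2 footnotes say only that it is done before and after the dose.

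**The concern.** A count of children who ever meet a criterion rises with the number of times each child is measured. If the number and lateness of readings differ by column, the percentages differ even when the drug does nothing. Vital signs and neurological examination are primary safety endpoints in both Parts (Protocol 6.1). The two previous-control columns hold the same children, first on sham and then on nusinersen, so readers will compare them directly. Nothing in SAP 5.4 aligns the readings or tells the reader that the monitoring differed.

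The neurological examination raises a separate, smaller question: whether findings at 4 to 6 h and findings at an unstated hour can share one post-dose row.

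**Working it through.** The documents give no total of readings, so there is no plan figure to reproduce. The counts below come from Protocol Tables 2, 3 and 4 and their footnotes.

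**Step 1. Scheduled post-procedure readings.**

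| Column | Sum | Total |
|---|---|---|
| Previous control, Part 1 (sham) | Day 1: 4; Day 2: 1; Day 15: 1; Day 29: 4; Days 64, 183, 302: 4 each | 22 |
| Previous control, Part 2, to Day 302 | Day 1: 4; Day 2: 1; Days 15, 29, 64, 183, 302: 1 each | 10 |
| Previous control, Part 2, to Day 778 | 10 + 4 (Days 421, 540, 659, 778) | 14 |
| Previous nusinersen, Parts 1 and 2 | 22 + 7 (Part 2 Day 1 and six later doses) | 29 |

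The gap of 12 between 22 and 10 arises on Days 29, 64, 183 and 302, at 3 readings each. Days 1, 2 and 15 have equal counts.

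With the planned 14 nusinersen and 7 sham children, Total averages (14 × 29 + 7 × 14) / 21 = 24 readings per child, against 22 for sham.

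**Step 2. All scheduled post-baseline readings.** SAP 5.4 says post-baseline, which also takes in later predose readings and the end visit.

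- Sham, Part 1: 22 + 5 predose + 1 end visit = 28.
- Previous control, Part 2, full schedule: 14 + 9 + 1 = 24.
- Previous nusinersen, both Parts: 28 + 7 + 6 + 1 = 42 (a repeated Part 2 Day 1 predose reading is not counted).
- Total: (14 × 42 + 7 × 24) / 21 = 36.

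**Step 3. What unequal counts do with no drug effect.** Assume each reading has the same independent chance p of meeting a criterion. Both p and independence are assumptions; the documents give neither. The chance that a child is ever flagged is 1 − (1 − p)^n.

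| p | n = 22 | n = 10 | n = 14 | n = 29 | n = 28 | n = 24 |
|---|---|---|---|---|---|---|
| 0.5% | 10.4% | 4.9% | 6.8% | 13.5% | 13.1% | 11.3% |
| 1% | 19.8% | 9.6% | 13.1% | 25.3% | 24.5% | 21.4% |
| 2% | 35.9% | 18.3% | 24.6% | 44.3% | 43.2% | 38.4% |
| 5% | 67.6% | 40.1% | 51.2% | 77.4% | 76.2% | 70.8% |
| 10% | 90.2% | 65.1% | 77.1% | 95.3% | 94.8% | 92.0% |

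Over equal dosing days (22 against 10) the previous-control pair differs by a factor of 1.4 to 2.1. On full schedules under the post-baseline rule (28 against 24) it narrows to 24.5% against 21.4% at p = 1%. The previous-nusinersen column runs the other way: 25.3% against 19.8% for sham at p = 1% on post-procedure readings. Total on post-procedure readings is (14 × 25.3 + 7 × 13.1) / 21 = 21.2% against 19.8%.

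**Step 4. Early stopping.** SAP 2 says sham children left Part 1 irrespective of planned dosing days and that Part 2 also ended early. A sham child whose last procedure was Day 29 was scheduled for 4 + 1 + 1 + 4 = 10 post-procedure readings; with Day 64 as the last, 14. Those equal Part 2 carried to Day 302 (10) and to Day 778 (14).

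**Step 5. Neurological examination.** Each Part schedules one post-dose examination per dose, and previous-control children have a Day 2 examination in both, so the counts match. The hour does not. Part 1 states 4 to 6 h. Part 2 states none, and the minimum stay is 1 h, except for the 24 h stay at a previous-sham child's first Part 2 dose.

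**The case against.** Five points can be made for the plan.

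- **Direction.** A reader might infer that the integrated sham-to-nusinersen safety contrast as a whole favours the drug. The documents do not support that. Only the previous-control pair leans that way. The previous-nusinersen column has more readings than sham, and Total is close to sham on post-procedure readings or above it on all readings (36 against 28). This stands.
- **Scope.** Other monitoring of previous-sham children is denser on nusinersen. To Day 302, safety laboratory tests fall on five Part 2 dosing visits (Days 15, 29, 64, 183, 302), against Days 64 and 183 plus End of Part 1. ECGs fall on Days 2, 29, 64 and 183, against Days 2 and 29 plus End of Part 1. Those differences work against the drug, so the point is limited to vital signs and the neurological hour. This stands.
- **Achieved data.** Both Parts stopped early, so the schedule does not show what was observed. This stands, and it leaves the sign of the achieved imbalance open.
- **Magnitude.** Readings hours apart in one child are unlikely to be independent, which probably makes the Step 3 differences too large. This stands; the figures are illustrative.
- **No formal contrast.** SAP 5.4 is descriptive, and a within-child comparison of Part 1 with Part 2 is also affected by age and disease course. The randomized arms share one Part 1 schedule, and Part 1 has its own analysis plan. All true, but the columns still appear side by side without disclosure of the monitoring difference.

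For the neurological examination, SAP 5.5 tabulates by post-dosing time point, so inflation through repeated looks does not arise. Only the mixing of hours remains.

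**Conclusion.** The concern holds in limited form. As written, SAP 5.4 lets monitoring intensity enter a primary safety display. After Part 2 Day 1 and Day 2, no post-dose reading later than 1 h is scheduled, and the columns carry 22, 10 to 14, and 29 scheduled post-procedure readings, or 28, 24 and 42 post-baseline readings on full schedules. Over equal dosing days, the previous-control pair could differ by a factor of 1.4 to 2.1 with no drug effect, for p between 0.5% and 10% and independent readings. The previous-nusinersen column is pushed the opposite way.

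The conclusion rests on scheduled counts and on the ever-flagged reading of SAP 5.4. It does not establish that the reported results will favour nusinersen: the achieved number of readings, and so the direction, cannot be read from the documents. The neurological part is a matter of unlike hours in one row, not of unequal counts.

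**What to change.** Keep the all-readings table, so that no late reading is lost. In SAP 5.4, add one table for the columns that cross Parts, restricted to matched time points. For the previous-control pair these are predose, Day 1 at 1, 2, 4 and 6 h, Day 2 at 20-24 h, and 1 h at later doses, with actual time since the procedure used for Part 1 Day 15. In every column of both tables, show the number of readings per child or a per-reading proportion. List the selected criteria in the same edit, since neither table can be reproduced without them.

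In SAP 5.5, put Part 1 (4 to 6 h) and Part 2 (hour not stated) post-dose findings in separate rows, not in one pooled post-dose time point.

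The cost is one extra table and some SAP wording. Visits, procedures and clinical conduct do not change.

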### **5.5 Neurological examinations**

Neurological items, comprising mental status, level of consciousness, sensory function, motor function, cranial nerve function, and reflexes, will be assessed. These assessments will be done at Screening, pre-dose, and post-dose.

The result collected for the majority of the tests is 'normal' or 'abnormal', however the assessment of sensations is reported as 'present' or 'absent' and the assessment of reflexes is captured on an ordinal scale. For each test, changes secondary to SMA will be recorded. For each test and post-dosing time point, the number and proportion of subjects who moved from 'Normal' to 'Abnormal'

will be presented, and the number and proportion who move from ‘Present’ to ‘Absent’ will be presented for sensations. For the assessment of reflexes, decreases (from pre-dosing 1 to post-dosing 0, 2 to 1. etc.) will be presented. Only changes not deemed secondary to SMA will be presented in the integrated analysis. The percentage of the different results for each test will be presented graphically by visit.

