9.3. Blinding Procedures

Part 1 of the study is a randomized, double-blind, sham-procedure controlled study. The Sponsor, parents and/or legal guardians, and key study site personnel will be blinded throughout Part 1 of the study. To maintain the study blind, it is imperative that subject treatment assignments are not shared with the subjects, their families, or any member of the study team, either at the study site or that of the Sponsor, except the unblinded site study staff (dedicated team) and the unblinded medical monitor or clinical research associate. The DSMB may be unblinded as described in the DSMB charter.

Before Part 2 Day 1, parents and/or legal guardians, key study site personnel, and the Sponsor will be unblinded to the treatment group to which the subjects were randomized in Part 1. This will be performed according to the unblinding plan, which will be finalized prior to unblinding. Of note, in the event that the Sponsor decides to rollover subjects to Part 2 early, unblinding for key study site personnel will occur prior to the End of Part 1 Evaluation in order to facilitate bringing subjects who were randomized to receive sham in Part 1 as soon as possible and to maintain the 4-month dosing interval for subjects who were randomized to receive Nusinersen in Part 2. Treatment in Part 2 will be open-label, and all study subjects will receive Nusinersen.

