16.2.2. Methods of Analysis

16.2.2.1. Neurological Examinations

Neurological examination findings will be listed for review, and as appropriate, results will be summarized descriptively for each treatment group. The number and percentage of subjects with shifts from baseline normal to each of the categorical values denoting normal, abnormal, and abnormal (not AE) will be summarized.

CONFIDENTIAL

The information contained herein may not be used, disclosed, or published without the written consent of Biogen MA Inc.

Note: If sedation was used, please allow sufficient recovery time for the subject to be fully engaged in the examination because change from baseline in neurological examinations outcome is a primary study endpoint. It is important that the data collected truly reflect the subject's neurological performance.

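### The integrated neurological change tables leave out changes attributed to SMA and all reflex increases, with no unfiltered shift table beside them and no statement of who makes the attribution or under what blinding

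*SAP*

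**What the plan says.** Protocol 16.2.2.1 states that "change from baseline in neurological examinations outcome is a primary study endpoint". It plans that "Neurological examination findings will be listed for review" and, as counts and proportions of children, that "shifts from baseline normal to each of the categorical values denoting normal, abnormal, and abnormal (not AE) will be summarized". It does not restrict this by presumed cause.

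SAP 5.5 counts, per test and post-dosing time point, moves from Normal to Abnormal and, for sensations, from Present to Absent. On reflexes it says: "For the assessment of reflexes, decreases (from pre-dosing 1 to post-dosing 0, 2 to 1. etc.) will be presented". On attribution it says: "For each test, changes secondary to SMA will be recorded". It then adds: "Only changes not deemed secondary to SMA will be presented in the integrated analysis". The section closes with a graph: "The percentage of the different results for each test will be presented graphically by visit".

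On blinding, Protocol 9.3 says: "The Sponsor, parents and/or legal guardians, and key study site personnel will be blinded throughout Part 1 of the study". The same section provides that, if rollover to Part 2 is early, key site staff are unblinded before the End of Part 1 Evaluation. SAP 1 and 1.3 record that Part 1 did stop early, and SAP 1.2 that Part 2 dosing was open label.

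SAP 2 sets four integrated safety columns: sham children in Part 1; the same children in Part 2, from their first nusinersen dose; nusinersen children across Parts 1 and 2; and a Total of the two nusinersen-exposed sets.

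**The concern.** The SAP puts a causal judgement between the examination and the table for a primary safety endpoint. A change that someone ascribes to the disease is not counted in the integrated summary, and nothing beside it shows how many changes were set aside.

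Two things are at stake. First, Protocol 5.1 describes SMA as loss of motor neurons with wasting of voluntary muscle. Motor worsening from any cause resembles the disease, so it is the kind of change most open to this attribution. Second, the judgement is not made under the same conditions in each column. If knowing the treatment alters the readiness to blame SMA, the columns can differ even when the true rates are equal.

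The reflex rule adds a smaller gap: an increase in a reflex grade would not be tabulated as a change at all.

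**Working it through.** **1. Is there a figure to reproduce?** No. Neither document attaches a rate to this endpoint, and SAP 8 states that there is no formal sample size calculation. The main check is therefore a comparison of text.

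**2. Planned analyses side by side.**

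| Item | Protocol 16.2.2.1 | SAP 5.5, integrated analysis |
|---|---|---|
| Starting state | Baseline normal | Normal (or Present); for reflexes, the pre-dosing grade |
| Filter by cause | None stated | Changes attributed to SMA left out |
| Reflex grades | No separate analysis | Decreases only |
| Who attributes, criteria, blinding | Not applicable | Not stated |
| Listing of findings | Planned | Not mentioned |

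**3. Blinding behind each integrated column.**
- Sham, Part 1: blinded, except possibly at an early End of Part 1 Evaluation.
- Previous sham, Part 2: wholly open label.
- Nusinersen, Parts 1 and 2: a mixture of the two.
- Total: the second and third combined.

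**4. Weight of one child.** Protocol 7.1 plans up to 21 children at 2:1, so 14 and 7. One child is 1/14 = 7.1 points in the nusinersen column, 1/7 = 14.3 in either sham column and 1/21 = 4.8 in the Total. These are planned maxima and assume that every child enrols and continues.

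**5. Illustration of the filter.** Let p be the true proportion of children who worsen and q the share of those changes attributed to SMA. The table then shows p(1 − q), and the chance that at least one change appears among n children is 1 − [1 − p(1 − q)]^n. The documents give neither p nor q; both are assumed here, with n = 14.

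| p | q = 0 | q = 50% | q = 75% | q = 90% |
|---|---|---|---|---|
| 20% | 95.6% | 77.1% | 51.2% | 24.6% |
| 10% | 77.1% | 51.2% | 29.8% | 13.1% |

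For example, with p = 20% and q = 75%: 1 − (1 − 0.05)^14 = 51.2%.

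**6. Illustration of unequal attribution.** Take an equal true rate of 30% in two columns and q = 50% where assessment is blinded, which shows 0.30 × 0.50 = 15%. If open-label q is 80%, that column shows 0.30 × 0.20 = 6%. If open-label q is 25%, it shows 0.30 × 0.75 = 22.5%. The direction depends on an unknown.

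**The case against.** The case for the SAP has real substance.

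- **Separating disease progression from other change is reasonable**, particularly once the sham control has ended. An unfiltered table will contain progression and will not undo open-label assessment. This stands, and it argues for showing both versions.
- **The data are not wholly hidden.** The by-visit graph has no stated filter or direction limit, and the protocol plans a listing. Adverse events are recorded whatever their relationship to treatment (Protocol 15.3.1) and tabulated across all relationship categories (SAP 5.1.6). This stands as mitigation. But the graph gives marginal percentages, so one child who worsens and one who improves cancel out. A listing is not a summary by group, and reporting an adverse event involves its own judgement.
- **The filter is stated for the integrated analysis only.** Part 1 has a separate SAP that was not available for this review, and no filter is stated for Part 2 output. This is correct. However, SAP 2 promises only limited Part 2 summaries, and Protocol 16 resets the Part 2 baseline at the first Part 2 dose. Part 2 output would therefore miss the nusinersen children's first exposure and any sham comparison.
- **The protocol's own table is limited.** It covers only shifts from a normal baseline, separates abnormal findings by adverse event status, and has no analysis of reflex grades. So the SAP cannot be said to drop a complete shift analysis that the protocol promised, and tabulating reflex increases goes beyond the protocol.

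A reader might also infer that the investigator makes the attribution. That is plausible, but SAP 5.5 names no one. Nor do the documents support sensory loss as something likely to be put down to SMA, since they describe a motor neuron disease.

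**Conclusion.** The point holds as a departure from the protocol in one set of displays. The integrated summary of a primary safety endpoint is restricted by a judgement whose author, criteria and blinding are unstated and which was made partly with treatment known. The protocol's shift analysis has no such restriction.

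It would be tempting to conclude that the whole endpoint is filtered, or that a drug signal is being concealed. The documents support neither: unfiltered routes exist, the share of changes removed is unknown, and the bias could favour or disfavour nusinersen. The probabilities above show only that moderate filtering matters with 14 children; they rest on assumed rates.

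The SAP's handling of other safety data supports the change. SAP 5.1.6 shows all adverse events and then the drug-related subset, and SAP 5.3 summarises ECG shifts with no filter for disease. The correction is a cheap improvement that should be made.

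**What to change.** In the integrated analysis of SAP 5.5:

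1. Tabulate all shifts from baseline normal as in Protocol 16.2.2.1, and Present to Absent for sensations, by the SAP 2 safety columns.
2. Tabulate reflex changes from baseline in both directions. The present wording compares pre-dosing with post-dosing grades while the endpoint is change from baseline, so state which reference applies.
3. Put the subset not attributed to SMA beside each of these, so that the number set aside is visible.
4. Footnote that the unfiltered version includes disease progression.
5. State who made the attribution and whether they were blinded at the time.

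SAP 5.5 already has the attribution recorded for each test, so no new data are needed. The cost is a few extra tables and some added text.
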